6. METHODS

6.1 Study parameters/endpoints

6.1.1 Main study parameter/endpoint

Feasibility will be judged according to two key questions:

1) Recruitment

What is the proportion of eligible patients who are willing to participate in this study and undergo an additional tumor biopsy?

2) Quality of tumor material

What is the percentage of tumor biopsies that can be examined successfully both at baseline and after 6 weeks of neo-adjuvant treatment?

We define a biopsy as successful if we collected enough tumor tissue and the quality of the tissue enables us to perform IHC-analysis to determine the infiltration of NK-cells into the tumor.

We conclude that our feasibility-study is successful if:

1. we achieve a recruitment rate of at least 20%.
2. we can examine biopsies successfully on infiltration of NK-cells (both on T0 and T1) in 14 of 20 patients (70%).

6.1.2 Secondary study parameters/endpoints

Preliminary treatment effects:

1. Changes in immune cell infiltration measured with tumor biopsy

Primary end-point for the preliminary effects is the alteration in number of NK-cells per total number of lymphocytes and in NK-phenotype.

Tumor tissue will be investigated by immunohistochemistry (IHC) to assess immune cell infiltration into the tumor with a specific focus on NK-cell frequency and phenotype.

Tumor tissue will be obtained with tumor biopsies. Tumor biopsies at diagnosis are performed as part of usual care. An additional tumor biopsy will be performed after 2 or 3 cycles of chemotherapy (6 weeks).

2. Immune function measured from blood.

Venous blood samples will be drawn prior to the start of chemotherapy and randomization (T0), and after 2 (3-weekly) or 3 (2-weekly) cycles of chemotherapy (T1). At T0 we will collect 20ml blood and at T1 we will collect 24ml blood to measure immune function. This 4ml extra blood on T1 is used to determine levels of leukocytes and thrombocytes prior to the biopsy. Immune cells will be investigated in whole blood using fluorescence activated cell sorting (FACS), to determine the frequency of CD4⁺ T cells, CD8⁺ T cells, regulatory T cells, B cells, monocytes, granulocytes, circulating dendritic cell (DC) subsets, myeloid derived suppressor cells, and the frequency, phenotype and function (i.e. cytotoxic potential, cytokine production capacity, and IL-6 and epinephrine receptor expression) of NK cells as demonstrated and reported previously [15].

3. IL-6 levels measured from blood

Patients included from the VUmc and randomized to the intervention group will be asked for consent to draw venous blood samples prior to and directly after one of the exercise sessions to examine acute responses to exercise. At both measurements we will collect 5ml blood. This will be done to measure Interleukine-6 levels (IL-6) which are supposed to be present in elevated concentrations during- and directly after exercise as outlined in the rationale for this study [16].

4. Physical fitness:

This will be assessed as secondary end-point to determine whether the exercise intervention yielded the expected physiological responses in 6 weeks.

- Aerobic fitness will be assessed during a submaximal endurance test performed on a cycle ergometer assessing the time that a patient can cycle at 70% of the estimated work load based on the steep ramp test, until a maximum of 30 min.[3]
- Upper and lower body muscle strength will be assessed with the 1RM leg press and bench press according to standardized protocols.

5. BMI

BMI will be calculated by dividing body weight by height (in meters) squared. Height will only be measured at baseline on a calibrated scale to the nearest 0.1 mm. Weight will be measured at baseline (T0) and T1 on a calibrated scale to the nearest of 0.1 kg.

6. Physical activity and health-related quality of life

Physical activity will be assessed with the Short Questionnaire to Assess Health-enhancing physical activity (SQUASH) and health-related quality of life with the EORTC QLQ-C30 (30 items) at baseline and after 6 weeks (T1).

6.1.3 Other study parameters (if applicable)

Exercise adherence:

Session attendance and compliance to the prescribed intensity, frequency and duration of exercises is monitored in exercise logs registered by the physical therapist. Patients in the exercise group are asked to keep an exercise log to register home-based exercise.

Demographic and clinical covariates

Information on smoking, alcohol intake, sociodemographic characteristics (e.g. age, ethnicity, education level, marital status), and exercise history will be obtained at baseline.

Clinical data:

- tumor characteristics (TNM-classification, degree of differentiation, hormone and Her2 receptor status)
- disease, treatment and treatment-related toxicity
- hospitalization
- performance status (ECOG)
- comorbidities (Charlson comorbidity index) and co-medication

Contamination is assessed from the control group at follow-up by a 3-item questionnaire, whether they changed their physical activity behavior and participated in structured exercise.

6.2 Randomisation, blinding and treatment allocation

After baseline assessment, patients will be randomized into the exercise or the control group by the use of a computerized random generator. Randomization is stratified for TNBC (yes/no), extent of disease (N+/N-) and treatment (regular versus dose-dense).

The researcher that examines the physical fitness will not be blinded to group allocation.

The pathologist and analyst that will examine the blood and biopsy tissue will be blinded to group allocation.

6.3 Study procedures

After providing informed consent (IC), patients will be randomized in either the intervention or waitlist control group.

Participants in the intervention group will attend supervised exercise sessions twice a week at a local physical therapist and are encouraged to be physically active for at least 30 minutes per day at Borg level 12-14 (see paragraph 5.1).

Participants in the control group are requested to maintain their usual daily physical activities and are offered supervised exercise sessions after 6 weeks at the expense of the study budget (see paragraph 5.1).

Study parameters will be assessed at baseline (before start of chemotherapy) and after 6 weeks of chemotherapy (2 3-weekly or 3 2-weekly cycles) in the patient's own treating hospital. When patients are included from the Amstelland hospital they will be asked beforehand to come to the Amsterdam UMC – location VUmc for the physical test, blood samples and biopsy. Consequently, Amstelland will be a recruiting hospital in this study.

During the visits, information on physical fitness and blood samples will be collected. In addition, during the visit on T1 a tumor biopsy will be obtained. The T1 biopsy and physical fitness test will not be performed on the same day, as this might lead to contamination of the results on immunoreactivity in blood and tumor. We will strive to perform the physical fitness tests prior to the 3th (3-weekly) or 4th (2-weekly) chemotherapy administration so patients don't have to come to the hospital an extra time.

The visit on T0 will last approximately 75 minutes, the first visit on T1 (biopsy and blood sample) approximately 30 minutes and the second visit on T1 (physical fitness test) approximately 45 min.

Questionnaires will be sent to the participant's home and will take up to 10 minutes to complete, based on 6 items per minute. Questionnaires will be sent in paper only. Table 1 presents a summary of all study parameters.

	Measurement tool	-1	T0	T1
Primary outcome measurement				
Recruitment		X		
Quality of tumor material	Tumor biopsy		X	X
Secondary outcome measurement				
Clinical data				
Extent of the tumor	Medical records		X	
Disease, treatment and toxicity	Medical records		X	X
Performance status	Medical records		X	X
Co-morbidities and co-medication	Medical records		X	
Physical tests				
Aerobic fitness	Steep ramp test & endurance test		X	X
Muscle strength	1 RM legpress and 1 RM bench press		X	X
BMI	Height		X	
	Weight		X	X
Blood sampling	Venous blood sample (20ml on T0, 24 ml on T1)		X	X
Tumor biopsy for determining preliminary effect	Tumor biopsy ¹		X	X
Questionnaires				
Physical activity	SQUASH (11-items)		X	X
Health-related QoL and symptoms	EORTC QLQ-C30 (30-items)		X	X
Sociodemographics, smoking & alcohol	6-items		X	
Contamination of control group ²	1-item			X
Exercise logs				
Adherence ³	Exercise log			X
Compliance ³	Exercise log			X

Table 1; Summary of measurements

¹This is the same biopsy as mentioned above (quality of tumor material)

² Parameter will only be assessed in the control group

³ Parameter will only be examined in physical therapists

Recruitment

The physician and/or nurse practitioner responsible for recruitment per participating center will be asked to keep a log and register the number of eligible patients (stage I-III breast cancer and scheduled for 2 or 3 weekly AC-treatment), the number of eligible patients invited for participation in the study and the number of eligible patients who declined participation. The physician and/or nurse practitioner will notify the coordinating researcher if patients received the study information and agreed to be approached by the coordinating researcher. The coordinating researcher will register the number of patients that declined to participate. Reasons for declined participation will be reported, as well as reasons for exclusion for study participation by both the physician/nurse practitioner and the coordinating researcher.

Tumor biopsies

The first tumor biopsy at diagnosis is performed as part of usual care.

The second tumor biopsy is for research purposes only and will be performed after 2 (3-weekly) or 3 (2-weekly) cycles of chemotherapy (6 weeks). Both biopsies will be performed in the patient's own treating hospital, except for patients from the Amstelland hospital which will take place at location VUmc.

Blood samples – immune system

The first blood sample of 20ml will be drawn prior to the start of chemotherapy and randomization (T0), and the second blood sample of 24ml after 2 (3-weekly) or 3 (2-weekly) cycles of chemotherapy (T1). The second blood sample will be taken before the biopsy to be able to determine levels of thrombocytes and neutrophils. In case values of thrombocytes are $\leq 50 \times 10^9/L$ and/or neutrophils (ANC) are $\leq 0.5 \times 10^9/L$, patients will be excluded for the second biopsy because of an increased risk of procedure related hemorrhage or infection. Blood samples will be collected in 10ml heparin tubes without gel. Both blood samples will be drawn in the patient's own treating hospital, except for patients from the Amstelland hospital.

Blood samples will be centrifuged and PBMC's will be isolated before storage at -80° in the Tumor Immunotherapy laboratory of the Cancer Center Amsterdam for the duration of this study.

Blood samples – IL-6

Patients included from the Amsterdam UMC and randomized to the intervention group will be asked for consent to draw blood samples prior to and directly after one of the exercise sessions to examine acute exercise responses. This will be done with an extra informed

consent form. If patients prefer not to participate in this extra blood sampling they will not be excluded from the study.

Patients will be asked to perform one of their exercise sessions in the VUmc. This session will be guided by an experienced physical therapist. Both before and after the exercise we will collect 5ml blood in a serum tube. This will be done to measure Interleukine-6 levels (IL-6) from serum which is supposed to be present in elevated concentrations during- and directly after exercise and is part of the rationale for this study.

Fitness tests

Physical fitness will be assessed both prior to randomization and after two cycles of chemotherapy in the patient's own treating hospital, except for the patients from the Amstelland hospital.

- Aerobic fitness will be assessed during a submaximal endurance test performed on a cycle ergometer assessing the time that a patient can cycle at 70% of the estimated work load based on the steep ramp test, until a maximum of 30 min [3].
- Upper and lower body muscle strength will be assessed using the 1-repetition maximum for leg press and bench press according to standardized protocols.

Questionnaires

- Physical activity will be assessed by the Short Questionnaire to Assess Health-enhancing physical activity (SQUASH). The SQUASH contains 11 items and measures the frequency, duration and intensity of 4 different physical activities (actively commuting, physical activity at work or school, household activities and leisure time activities).
- Health-related Quality of Life (HRQoL) will be assessed by the European Organization Research and Treatment of Cancer Quality of Life Questionnaire (EORTC QLQ) Core on baseline and after the intervention (T1).
- A questionnaire on demographic and clinical covariates will be assessed on baseline. This questionnaire includes questions about smoking, alcohol, exercise history and sociodemographic characteristics (e.g. age, ethnicity, education level, living situation).

Clinical data

Clinical data will be obtained from medical records on baseline, during and/or after the intervention. This includes information on extent of the tumor, disease, treatment and treatment-related toxicity, hospitalization, performance status (ECOG), comorbidities and co-medication.

Exercise logs

To collect data on adherence and compliance to the exercise, physical therapists will be asked to register data in exercise logs. These exercise logs will be collected at T1 by the researcher.

If this pilot-trial determines feasibility, we will strive to set up a sufficiently powered RCT. In that case, data collected in this pilot trial might be used as part of the data collection of this next RCT. Patients will be asked for consent to use the coded data (not the human material) for this next RCT.

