3. STUDY DESIGN

This is a multicenter randomized controlled feasibility trial, in which 20 women with breast cancer scheduled for neoadjuvant 2 or 3 weekly AC-T(H) chemotherapy will be randomized into a combined aerobic and resistance exercise intervention group or a usual care (no exercise)

control group, during the first 6 weeks (2 or 3 cycles) of chemotherapy. Patients from the control group will receive care as usual and are requested to maintain their usual daily physical activities. In order to limit contamination (increase of exercise in the control group), non-participation and prevent dropout, the control group will be offered the same 6-week exercise intervention after the tumor biopsy has been taken after 6 weeks. The study design and timepoints of measurements are presented in Figure 2.

[figure not shown]

Figure 2. Study design and time-point of measurements

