5. TREATMENT OF SUBJECTS

5.1 Investigational product/treatment

Exercise intervention

Patients in the exercise-group will follow a combined resistance and aerobic exercise program that was proven beneficial for physical fitness, fatigue, quality of life and chemotherapy completion rates in patients with breast cancer receiving adjuvant treatment [3]. This program meets the American College of Sports Medicine's exercise recommendations for patients with cancer¹¹. Exercise sessions take place 2 times per week for 60 min and include aerobic and resistance exercises at moderate-to-high intensity, in which the adequate training load will be tailored to a patient's individual fitness level throughout the intervention [3]. After a short warming-up (5 min), patients perform muscle strength exercises for 20 min per session, starting with two series of 12 repetitions at 70% of the one repetition maximum (1RM) per exercise and increasing gradually to two series of eight repetitions at 80% 1RM. The resistance program consists of at least six exercises targeting the large muscle groups with vertical row, squat, bench press, pull over, abdominal crunch and lunge. Aerobic exercises are performed for 30 minutes per session (with a minimal duration of ten minutes per exercise), with an intensity of 50% to 80% of the maximal workload (Wmax) as estimated by the Steep Ramp Test (SRT). The intensity of aerobic exercises is increased if a patients scores a 12 or lower on the Borg scale of perceived exertion, while the intensity is decreased at a score of 16 or higher. The heart rate should be

within a heart rate zone of 60% to 90% of the maximal heart rate, which is conventionally estimated as 220 minus age [3].

Exercise sessions are supervised by a specially educated physical therapist via the OncoNet network (www.onconet.nu) allowing patients to train close to their homes [3].

Additionally, patients are encouraged to be physically active for 30 minutes on at least 3 other days in the week at Borg level 12-14.

Patients in the exercise group are asked to keep an exercise log to register home-based physical activity.

Usual care group

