Patients from the control group will receive care as usual and are requested to maintain their usual daily physical activities. In order to limit contamination (increase of exercise in the control group), non-participation and prevent dropout, the control group will be offered the same 6-week exercise intervention after the tumor biopsy at T1 at the expense of the study-budget.

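### Section 6.3 keeps T1 blood and biopsy off the fitness-test day but not off supervised-session days, which only the exercise arm has before T1, so an acute blood NK shift could pass for a 6-week effect

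*Protocol*

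**What the plan says.** Section 6.3 sets one separation at T1: "The T1 biopsy and physical fitness test will not be performed on the same day, as this might lead to contamination of the results". The reason it gives concerns immune readings in blood as well as in tumor. It then describes two T1 visits: "the first visit on T1 (biopsy and blood sample) approximately 30 minutes and the second visit on T1 (physical fitness test) approximately 45 min". Blood is therefore taken at the biopsy visit and is also kept off the fitness-test day. The fitness test is aimed "prior to the 3th (3-weekly) or 4th (2-weekly) chemotherapy administration".

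For the exercise arm, section 5.1 says: "Exercise sessions take place 2 times per week for 60 min". Section 3 places the programme "during the first 6 weeks (2 or 3 cycles) of chemotherapy". Home activity is encouraged as well. Controls keep their usual activity and are "offered the same 6-week exercise intervention after the tumor biopsy at T1", so before T1 the programme belongs to one arm only.

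Sections 6.1.2 and 6.3 tie T1 blood and biopsy to the number of completed chemotherapy cycles. Neither ties them to the last exercise session.

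**The concern.** The separation covers exertion that both arms undergo, the fitness test, and leaves uncovered exertion that only one arm undergoes before T1, the supervised session. For a between-arm comparison the second matters more. The protocol's own rationale (section 1) reports that, in healthy people, NK cells start to enter the circulation minutes after exercise begins. Section 6.3 also measures an acute IL-6 response around a single session, so the investigators already treat acute responses as a separate question.

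If a T1 sample follows a session closely, the blood NK measures in the exercise arm could mix an acute response with the 6-week training response. The safeguards in the plan do not separate the two. Blinded reading of samples (section 6.2) does not change what is in the tube. Adjustment for the baseline value (section 8.2) cannot remove an exposure that arises after randomisation and differs by arm.

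At stake are the exploratory blood NK results. Sections 4.4 and 8.2 plan a sample-size calculation from observed effects, so an acute component could also carry into planning of the next trial.

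**Working it through.** The plan states no figure on this point, so there is none to reproduce. The check covers timing first, then scale.

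**1. Is there any gap rule?** Sections 3, 5.1, 6.1.2 and 6.3 give T1 as after 2 three-weekly or 3 two-weekly cycles, or 6 weeks. None gives an interval after the last session. The nearest statement is in the questionnaire part of section 6.3, which places the quality-of-life measurement "on baseline and after the intervention (T1"). That implies training is over by T1 but not by how long, and it concerns a questionnaire rather than the blood draw.

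**2. Could T1 sampling fall close to a session?**
- Three-weekly: 2 × 21 = 42 days, so the 3rd administration is on day 43, counting the first as day 1.
- Two-weekly: 3 × 14 = 42 days, so the 4th administration is also on day 43.
- If the fitness test is the second T1 visit and falls on or before day 43, blood and biopsy, on a different and earlier day, fall on day 42 or before.
- If the 6-week programme starts on day 1, it runs to day 42. Sampling would then fall at the edge of week 6.

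This is an inference. It needs cycles given on time, visit labels that reflect order, and a programme that starts with chemotherapy. The start day is not stated, and the fitness-test timing is only an aim.

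**3. Share of exercise-arm T1 samples on a supervised-session day.** Inputs: 2 sessions a week (section 5.1) and 20 patients in two arms (section 3). The allocation ratio is not stated, so 10 per arm is assumed.

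| Situation | Formula | Share | Patients of 10 |
|---|---|---|---|
| Programme ended before T1 | – | 0% | 0 |
| Training runs to T1, dates unrelated to sessions, full attendance | 2/7 | 29% | 2.9 |
| As above, half of those sessions held before the draw | 0.5 × 2/7 | 14% | 1.4 |
| As above, attendance assumed 75% | 0.75 × 0.5 × 2/7 | 11% | 1.1 |

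Only sessions held before the draw matter, so the last two rows are nearer to the exposure at issue than the second.

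**4. From exposure to bias.** With no true 6-week effect, the apparent arm difference is roughly (share affected) × (mean acute shift in affected samples), less any like contribution from controls' usual activity. The protocol gives neither the size nor the duration of the shift, so the product cannot be evaluated.

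**5. Could existing data correct it later?** Session logs and home-exercise logs cover the exercise arm and are not stated to record clock time. SQUASH and the control-arm contamination questionnaire (sections 6.1.2 and 6.1.3) are not stated to capture when the patient last exercised before the draw. A later analysis plan cannot recover a time that was not recorded.

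**The case against.** The strongest reply is that the exposure may not occur. The programme lasts 6 weeks, measurements follow 6 weeks of chemotherapy, and one passage puts T1 after the intervention. This stands: 0% is a real possibility, and the short gap is inferred.

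Second, section 6.3 names only the fitness test and does not say that ordinary training contaminates results. This also stands. A reader might infer that the protocol contradicts itself; it does not. It leaves a gap in a precaution it has chosen to take.

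Third, the rationale says how quickly NK mobilisation starts, not how long it lasts. If it is short-lived, only exercise shortly before the draw matters. That limits the claim to what could happen.

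A reader might also infer that home activity puts most or all samples at risk, because section 6.3 says patients "are encouraged to be physically active for at least 30 minutes per day at Borg level 12-14". The documents do not support that. The activity is encouraged rather than scheduled, it may follow the draw, and section 5.1 describes it differently, as at least 3 other days a week (the two sections should be reconciled). Nor could a ban on all same-day programme exercise be met on the per-day wording while the programme stays as it is.

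Finally, the lead preliminary-effect endpoint is NK cells in tumor (section 6.1.2), and the planned larger trial is about tumor infiltration (section 8.1). A reader might extend the concern to the biopsy result. The documents leave that uncertain, because movement of NK cells into tumor is part of the hypothesised effect.

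**Conclusion.** The point holds in a limited form. Section 6.3 separates T1 sampling from exertion shared by both arms and does not separate it from supervised sessions that only the exercise arm has before T1. As written, the plan allows a T1 blood sample to follow a session on the same day, and an acute NK shift could then be read as a 6-week effect in the blood analyses.

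The exposed share runs from 0% to about 29% of exercise-arm samples, or about 14% if half of the sessions precede the draw. The non-zero figures assume that training continues up to T1 and that appointment dates are unrelated to session days. They describe exposure and are not a bias estimate. Controls' usual activity makes this a difference of degree between arms.

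The consequence is confined to exploratory blood measures in a trial that is underpowered by design for effects. The recruitment and biopsy-quality criteria in section 6.1.1 are unaffected. This is a cheap improvement, not a flaw that undermines the trial. It belongs in the protocol because it governs when samples are taken and what is recorded.

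**What to change.** Extend the existing sentence in section 6.3 so that T1 blood and biopsy are also not scheduled after a supervised session on the same day, and are taken before any home activity that day where possible. Leave any longer interval to the investigators. Achieve this through the choice of appointment, with the exercise programme and the controls' usual activity unchanged.

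Add one item to the T1 sampling form in both arms: date and time of last exercise. Use it for a sensitivity analysis of the blood NK measures, for example by repeating the baseline-adjusted comparison without samples taken soon after exercise.

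Cost: some T1 appointments must be planned around session days, for which the study team needs the session dates, and there is one extra data field for 20 patients.
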